Primary outcome measures: (1) Proximal effects of CBT and ACT messages in the JITAI group: decreases over 20-minute intervals in craving and negative mood, with increases in self-efficacy; (2) strategy-situation fit in the JITAI group; (3) group differences in distal effects of treatment (week 11 versus week 2) in terms of self-efficacy and coping flexibility.

Secondary outcome measures: (1) Trait predictors of differential responses to CBT and ACT, in the JITAI group; (2) group differences in frequency of opioid-positive urine over time; (3) time courses of responsiveness to ACT vs. CBT, in the JITAI group; (4) whether the intervention types that benefit participants most when “pushed” by the app are the same ones participants choose when subsequently given the opportunity to “pull” interventions.

B. Table of Contents

A. Précis.....	2
B. Table of Contents.....	4
C. Background.....	5
1. From mobile assessment to mobile treatment: a microrandomization approach	5
2. Momentary interventions to be tested in the first arm of this protocol.....	7
3. Two ways to deliver a momentary intervention: push versus pull.....	9
4. Rationale for a multiple-arm protocol.....	10
D. Study objectives	10
E. Study design and methods	11
1. Overview of arm 1.....	11
2. Arm 1, Phase 1: Formative interviews.....	12
3. Arm 1, Phase 2: Clinical trial with microrandomization.....	12
F. Inclusion and exclusion criteria	24
1. Inclusion criteria.....	24
2. Exclusion criteria.....	24
G. Clinical and laboratory methods	25
H. Collection and storage of human specimens or data.....	30
I. Statistical analysis.....	31
1. Outcome measures.....	31
2. Analysis of study outcomes	31
3. Criteria for statistical significance.....	34
J. Required sample size	35
K. Plans for enrollment at multiple sites.....	36
L. Human-subjects protection plan	36
1. Rationale for subject selection based on gender/ethnic/race categories at risk.....	37
2. Recruitment plan	37
3. Justification for exclusion of vulnerable populations	38
4. Evaluation of risks/discomforts and benefits ratio	39
5. Subject monitoring	43
6. Conflicts of interest.....	44
M. Protection of participants' privacy and confidentiality	45
N. Study agents/interventions.....	45
O. Plan for reporting unanticipated problems and adverse events.....	45
P. Data and safety monitoring	45
Q. Clinical monitoring plan.....	46
R. Data/records management	46
1. Quality assurance.....	46
2. Relationship to other protocols	47
3. Data-sharing description.....	47

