Collection of data from incarcerated participants will not be an issue, because, like other personal property, the devices will be routinely confiscated by prison authorities upon entry and not returned until the prisoner is released. If the devices are returned to us and they somehow do contain data from time during incarceration, we will delete those data.

On some occasions, initiation of mobile data collection will begin later than scheduled. This typically occurs when the participant cannot meet with the experimenter at the appropriate time to receive the necessary introduction to the experimental condition. In all cases, all data collection will start as close as possible to the protocol schedule.

A 21-day taper will be offered to OBOT participants who choose to withdraw voluntarily from the study. Participants will also be discharged (with a 21-day taper for OBOT participants) if they meet one or more of the following termination criteria: (1) missing 4 (OBOT) or 3 (TE) study visits; (2) on 6 occasions, bringing in a dead smartphone following a missed clinic visit; (3) violating clinic rules; (4) failing to comply with smartphone data collection; or (5) losing or damaging two smartphones. In some cases, where disruptive behavior is a risk to staff or other participants, the OBOT taper may be less than 21 days. Any taper, whether administrative or voluntary, will include take-homes for Saturdays and Sundays.

H. Collection and storage of human specimens or data

Electronic data will be stored on the NIDA IRP's secure, password-protected system of electronic medical records (Clinical Data Warehouse; CDW). Paper records are stored in the Archway clinic under double lock in an area where individuals who are not part of the study staff do not have access (BRC building; room number 01B605). After the study is completed and data have been analyzed, the paper records will be stored at an NIH-approved commercial facility for the storage of sensitive data until approval for their disposal has been given.

Audio from the formative interviews will be sent without identifiers to a HIPAA-compliant professional transcription service. These services typically transcribe medical records. We will not permit the service to keep or share data. We will keep the transcripts indefinitely on secured servers. The audio will be accessible only to investigators and will be deleted when all interview data have been summarized—most likely within a year.

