Stored biological specimens will be kept in a secure freezer in the Archway's NIDA freezer room until they are analyzed (BRC building; room 01B405). Specimens may be used for future analyses not described in the current protocol, but only after approval from the IRB. Any unplanned loss or destruction of the samples will be reported by the PI to the IRB.

Participants will be given the option of having their samples destroyed and/or having their data deleted, with the caveat that this might not be possible if the samples or data have already been shared (in an IRB-approved collaboration) with other researchers.

I. Statistical analysis

1. Outcome measures

Formative-interview phase

We are not using standardized questionnaires for the formative interviews, nor *a priori* cutoffs for outcome. Instead, this phase will be an iterative, collaborative process in which interviewees help us determine the extent and nature of changes to the content and interface of the JITAI app. We will replace any content (or interface elements) that multiple interviewees find confusing, unhelpful, or inappropriate. Any changes resulting from the formative interviews will, of course, be reflected in an amendment that the IRB will review.

As we note below, in the section on “gender/ethnic/race categories at risk,” focus-group data collected by another team of investigators in Washington, DC, show that low-SES African-American clinic attendees find mindfulness exercises helpful and empowering (Spears et al., 2017). This is an encouraging finding. A major purpose of our formative interviews will be to help ensure that our JITAI intervention is viewed similarly by the diverse groups of people for whom we intend it. If we notice any tendency for responses to differ by race, sex, or socioeconomic status, we may submit an amendment to expand the formative-interview phase.

Microrandomized trial

Proximal outcome measures (JITAI group only)

Decreases in problems in the 20 minutes from “pre” to “post” assessment
Ratings of usefulness at “post” assessment.

Distal outcome measures (JITAI group vs. EMA group)

FIT-60 mindfulness questionnaire (week 2 vs. week 11)
DTCQ for coping self-efficacy (week 2 vs. week 11)
COPE for coping-style flexibility (week 2 vs. week 11)
MCQ for delay discounting (week 2 vs. week 11)
Need for Closure scale (week 2 vs. week 11)
TSPQ-21 for Twelve-Step Involvement (week 2 vs. week 11)
opioid and other drug use (3x/week urine tests throughout study)

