Other aspects of strategy-situation fit to be tested will include the setting (e.g., home, work, obligations, recreation), the nature of the problem (e.g., craving, boredom, anger), and cue exposure ("People, places, or things' are reminding me of drugs"). We will also examine alternative ways of operationalizing the controllability of a situation, because we know of no standardized way of doing so. In particular, we will examine the escapability of a situation in conjunction with its desirability, incorporating items such as "The place where I am is pleasant and comfortable (not too hot/cold, noisy, ugly, dangerous, etc.," "What I'm doing right now is

enjoyable for me,” and “What I’m doing right now is important to me.” We do not have *a priori* hypotheses for these analyses, and we will state that clearly when we report them.

Hypothesis 3, distal: Main effect of intervention (the group randomized to JITAI will have better outcomes—e.g. less drug use, higher self-efficacy, a greater increase in flexibility of coping styles—than the EMA-only control group when assessed at week 11).

These analyses, unlike the preceding ones, will use data from both the JITAI group and the EMA control group.

For group differences in mindfulness (FIT-60), coping self-efficacy (DTCQ), and coping-style flexibility (COPE), we will use analyses of covariance (ANCOVAs); in each ANCOVA, the dependent variable will be the score on the relevant measure at week 11, the categorical predictor will be group (JITAI vs. EMA) and the covariate will be the score at week 2.

The analyses on those questionnaire responses can be done only for participants who reach week 11. However, we will also test for a group difference in opioid use (thrice-weekly urinalyses) across the duration of the study. This analysis will use a generalized linear mixed model, so missing data (whether from early dropout or missed visits) will result in appropriately adjusted standard errors.

For a more stringent assessment of drug-use outcome, we will also compare the proportion of participants in each group who “succeed” in treatment (by completing week 11 and testing opioid-negative that week). Cessation of opioid use is not the main outcome measure for this study; we are more interested in psychological changes that might plausibly lead to good long-term outcomes. Nonetheless, we will assess and report this measure of treatment response.

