For each participant in the JITAI group, we will use multilevel models with person-specific slopes to quantify the relative overall effectiveness of CBT vs. ACT messages during the “push” weeks, in terms of proximal changes craving, self-efficacy, and/or mood. We will then calculate the participant’s relative overall preference for CBT vs. ACT content during the “pull” week. These can be straightforwardly shown in a scatterplot with an accompanying bivariate correlation coefficient.

3. Criteria for statistical significance

The criterion for statistical significance will be set at $p \leq 0.05$, two-tailed. For hypothesized effects that do not reach statistical significance, we will calculate Bayes factors (Dienes, 2014), which help determine whether “nonsignificant” findings favor the null or the alternative hypothesis or whether they should be considered inconclusive.

J. Required sample size

For the formative-interview phase, we anticipate that 30 interviewees will be sufficient to give us feedback on our prototype materials and app interface. We may revisit this if we find that responses are highly variable across interviewees. We expect that most people who agree to be interviewed will provide usable information, so we are setting out enrollment ceiling at 35.

For the microrandomized trial, which is longer and more demanding, we expect a higher rate of dropout. We will enroll up to 150 participants to reach a target of 85 (50 JITAI, 35 EMA control) who complete the week-eleven outcome assessment. The calculations that led us to that total are as follows.

For hypothesis 1 (the proximal main effect of messaging in the microrandomized trial), we used a power-and-sample-size calculator <<https://pengliao.shinyapps.io/mrt-calculator/>> developed specifically for microrandomized studies (Liao et al., 2016). This calculation applies specifically to the JITAI group, not the EMA control group. As Liao et al. (2016) point out, there is very little precedent for determining what a proximal effect size should look like, but small studies with microrandomized designs can often detect seemingly small effects, on the order of $d = .15$. We decided that the most important consideration was to set our beta level high (.90, rather than the conventional .80), and we started by entering the following assumptions:

Days of study: 56 [eight weeks of “push” intervention].

Number of decision time points per day: 4.

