A meta-analysis we cited earlier suggested effect sizes on the order of .57 for a smartphone intervention versus standard treatment (Lindhiem et al., 2015). For some of the comparisons of interest here, such as expansion of the repertoire of coping strategies, group differences are likely to be even larger, because our control condition will not include any instruction relevant to them. With evaluable data from 50 participants in the JITAI group and 35 in the EMA control group, we will have power of .90 (in two-tailed tests) to detect a group difference of $d = .70$ or larger in any overall outcome. At the more conventional beta of .80 (in two-tailed tests), we will have power to detect a d of .60 or larger.

K. Plans for enrollment at multiple sites

Not applicable.

L. Human-subjects protection plan

1. Rationale for subject selection based on gender/ethnic/race categories at risk

Participant selection will be equitable, without regard to nationality, sex, race, religion, or creed. The anticipated racial/ethnic and sex distribution will reflect that of the local community and drug-using population.

The use of mindfulness interventions in the US might seem, on its face, like a trend that would appeal primarily to a culturally or economically privileged few. In fact, however, focus-group data from Washington, DC, show that low-SES African-American clinic attendees find mindfulness exercises helpful and empowering (Spears et al., 2017). Lessons learned from those prior focus groups, and from the formative interviews we do, will help shape our interventions.

2. Recruitment plan

Recruiting

Standard recruitment efforts employed by MMG will be used for this nonresidential treatment study (See NIDA/IRP Medical Policy and Procedure Manual). MMG advertises extensively in a variety of newspapers that are read by both sexes and all ethnicities. Special outreach efforts are made toward women and minorities.

Ads will be submitted to the IRB for approval before they are used.

Our experience with OBOT and TE patients in the 020 protocol is that we enroll each type at a rate of about 4 every 30 days. If that rate (8 enrollees every 30 days) is maintained, we should reach our enrollment target of 175 in just under 660 days, with roughly equal numbers of OBOT and TE participants.

Screening methods

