A. Parameters monitored: Because each patient is to be seen at Archway three days a week, any events can be readily noted: nurses routinely ask patients if they are experiencing any new health problems and record all adverse events. Under our current system, the nurses make weekly entries into NIDA/IRP's Clinical Data Warehouse (CDW, a Microsoft SQL Server database) including patient identifying information, the nature of the problem, date reported, date of onset, expectedness, seriousness, relatedness to the intervention, action taken, and outcome; the MAI can update and clarify this information, but cannot delete it.

Periodically, the MAI reviews the adverse-events information, noting any trends and reporting them to the IRB as appropriate. Patients' weight will be measured once per month; other vital signs may be taken to assess changes in participants' clinical condition. As part of usual Archway procedures, we routinely collect data on attendance, urine-test results, opioid-withdrawal symptoms, other subjective and psychological effects, and requests for dose

changes. The physician will review all lab results and make referrals and recommendations as appropriate.

B. Criteria for individual subject withdrawal/termination

Nonmedical criteria for termination. Participants will be discontinued from the study if they: (1) miss 4 study visits (OBOT) or miss 3 visits (TE, no taper as these participants do not receive treatment at Archway); (2) violate clinic rules; 3) fail to comply with EMA data collection; or (4) lose or damage two smartphones. Participants receiving OBOT from us will be offered a 21-day taper and assisted in finding a treatment provider in the community.

Participants receiving OBOT from us will be discontinued from the study possibly without a taper if they miss 3 consecutive scheduled visits.

Participants will be discontinued from the study (possibly with a taper of less than 21 days, which might not be at Archway) if they: (1) are rude and/or disruptive to the staff or to other patients; (2) try to buy or sell drugs on clinic or hospital property; (3) deface or damage clinic property; (4) try to tamper with a urine sample (for instance, by bringing urine from home, or by adding something to the urine).

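### Adjusted standard errors do not protect the opioid-urine comparison if urines are lost for reasons tied to unseen use; the missing-data assumption should be stated and tested by arm and discharge reason

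*Combined protocol and SAP*

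**What the plan says.** Section I.2, Hypothesis 3, notes that the questionnaire analyses need participants to reach week 11. It then adds a comparison of opioid urines across the whole study by generalized linear mixed model, so that "missing data (whether from early dropout or missed visits) will result in appropriately adjusted standard errors". The plan states no missing-at-random assumption, no rule for urines due after discharge and no sensitivity analysis of this model. The next paragraph of I.2 adds a stricter comparison: the proportion who complete week 11 and are opioid-negative that week. The Précis lists the urine comparison as secondary, and I.2 says that stopping opioid use is not the main outcome.

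Discharge rules for both arms:
- Section G, Other procedural issues, lists "missing 4 (OBOT) or 3 (TE) study visits" among the termination criteria.
- Section L.5.B adds discontinuation of those who "try to tamper with a urine sample (for instance, by bringing urine from home, or by adding something to the urine".

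Rules that bear on the JITAI arm only:
- Sections E.3 and G require all 16 Deep Dives within 21 nights, with discharge otherwise.
- Section G counts an entry toward the 82% requirement only if both the *pre* and the *post* assessment are done. Section E.3 gives the EMA arm the *pre* assessment alone.

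On numbers, Section J says "We will enroll up to 150 participants to reach a target of 85 (50 JITAI, 35 EMA control".

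**The concern.** A likelihood-based mixed model uses each participant's observed urines. It gives a valid group contrast if, given those urines and a correct model, the chance of a urine being missing does not depend on its unseen result. If people stop attending, or are discharged, because of use that no urine has yet recorded, that condition fails. The estimate itself then moves, and the standard error carries no information about the movement.

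This trial is exposed because several routes out could be connected with use. Missed visits may follow relapse, and tampering is an attempt to hide the outcome being measured. If such loss is alike in both arms, the main risk is that a real benefit is diluted. If it differs by arm, the contrast can move in either direction, including a false advantage for JITAI. At stake is the one between-group drug-use analysis that does not require reaching week 11.

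**Working it through.** **1. The plan's own figure.** Section J claims power .90 at d = .70 with 50 and 35 evaluable. The noncentrality is 0.70 × √(50 × 35 / 85) = 3.176, and Φ(3.176 − 1.960) = 0.888 (0.881 with the t distribution). This agrees with .90 within 2 points and is not in dispute. It counts evaluable participants and says nothing about lost urines.

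**2. How much could be missing.**
- Non-completion allowed for: (150 − 85)/150 = 65/150 = 43.3%.
- Scheduled urines: 3 × 11 = 33 each, and 150 × 33 = 4,950 in all.
- If non-completers lose half their urines (assumption): 65 × 33 × 0.5 = 1,072, or 21.7%. If they lose a quarter or three quarters: 10.8% or 32.5%.
- Isolated misses are capped by the visit limits. With equal OBOT and TE numbers (expected in Section L.2) and the limits enforced, the cap is 85 × 2.5 + 65 × 3.5 = 440. After-exit urines are then at least 1,072/(1,072 + 440) = 71% of those missing (55% and 79% for the quarter and three-quarter cases). Section G makes missed-visit discharge discretionary in one place and mandatory in another. Those passages need reconciling.
- Deep Dives start in week 3, so 21 nights end with week 5. A JITAI participant discharged under that rule loses at least weeks 6–11: 6 × 3 = 18 of 33 urines.

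**3. Crude rates, for orientation only.** Let m be an arm's missing share and e the excess positivity of its missing urines over its observed ones. The observed rate is too low by m × e, so the difference is off by m_J·e_J − m_E·e_E. With equal m and e this is 0. Suppose dropout is 52% vs 31% (88 × 0.52 + 62 × 0.31 = 65), half the urines are lost, and e is 10 to 40 points. The difference is then (0.26 − 0.155) × 10 to 40 = about 1 to 4 points in favor of JITAI. All these rates are assumed. This is not the mixed model's bias, because the model conditions on each person's earlier urines.

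**4. Simulation of the model.** The set-up was 150 participants split 50:35 (88 JITAI, 62 EMA), 33 visits, discharge at 3 or 4 misses, a random-intercept logistic model with a group term, and 150 runs per row. Assumed rates: relapse hazard 2% per visit (multiplied by e^−0.9 in JITAI where there is an effect); baseline log odds −1.4 with intercept SD 1; relapse adds 2.5. Missed visits were 9% throughout when unrelated to use, otherwise 4.5% before and 35% after relapse. JITAI-only discharge per visit was 25% if relapsed and 0.4% if not (visits 7–16), then 15% and 0.2%.

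| Loss mechanism | True effect | Log OR, all urines → observed | SE | Rejection |
|---|---|---|---|---|
| Unrelated to use | no | 0.00 → 0.00 | 0.216 → 0.221 | 3% → 3% |
| Unrelated to use | yes | −0.38 → −0.33 | 0.210 → 0.215 | 46% → 33% |
| Relapse-linked, alike in both arms | no | −0.02 → −0.01 | 0.216 → 0.197 | 7% → 8% |
| Relapse-linked, alike in both arms | yes | −0.40 → −0.24 | 0.211 → 0.194 | 45% → 21% |
| Same, plus JITAI-only discharges | no | −0.01 → −0.12 | 0.217 → 0.195 | 7% → 11% |
| Same, plus JITAI-only discharges | yes | −0.38 → −0.26 | 0.210 → 0.192 | 49% → 26% |

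Monte Carlo standard errors are 0.005 to 0.009 for the shifts and about 1.5 to 4 points for the rejection rates, so 7% vs 11% is only suggestive. The fitted model has no time term. That may be why even unrelated loss moves a true effect by about 0.04, and that much of the 0.16 attenuation in the fourth row need not be due to informative loss. In every use-linked row the standard error fell, so it gave no warning.

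**The case against.** The strongest reply is that the plan already has an analysis in which discharge is not ignored: anyone who leaves before week 11 fails the success criterion. That stands in part. But it looks at one time point, it charges JITAI for its own extra discharge rules, and it does not test the mixed-model estimate.

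A reader might infer that the missed-visit and tampering rules by themselves tilt the comparison toward JITAI. The documents do not support that. Both rules apply to both arms, and the 3-versus-4 limit divides TE from OBOT, not JITAI from EMA. In the simulation they produced no shift under no effect and a conservative one under a true effect.

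A reader might also take 43% as the forecast loss. It is not: 150 is a ceiling (Sections F.1 and J), and Section P stops the study once the target number of completers is reached.

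It is also fair that the model handles dropout predicted by earlier positive urines, that urine collection is observed and tampering may be rare, that the documents nowhere say missed visits follow use, and that the outcome is secondary. These points limit the size of the concern. None of them makes adjusted standard errors a safeguard against bias.

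**Conclusion.** The concern holds in a limited form. The sentence in I.2 offers the wrong protection: the validity of the urine comparison rests on an unstated missing-at-random assumption. That assumption is open to doubt here, with up to 43% non-completion allowed for and discharge rules that may be related to use.

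The size and direction of any bias cannot be derived from the documents. Under the assumed rates above, loss alike in both arms shrank a true log odds ratio from −0.40 to −0.24. Adding JITAI-only, use-linked discharges gave a spurious −0.11 when there was no effect. A different link between use and attendance could make either figure negligible. It would be tempting to conclude that the result will be biased in favor of JITAI, or by a stated number of percentage points. Neither follows: the JITAI-only rules make arm-dependent loss plausible, but they bias the contrast only if falling foul of them is related to unseen use. Because the outcome is secondary, this should be corrected before analysis but does not undermine the trial's primary aims.

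**What to change.** - Replace the standard-error sentence with an explicit statement that the mixed model assumes missingness depends only on observed data. Keep the model as the main analysis.
- Tabulate missing urines and discharge reasons by arm.
- Prespecify a delta-adjusted (tipping-point) analysis over scheduled urines through week 11. Shift the log odds of a positive result for missing urines, starting from zero (missing at random). Let the shift differ by arm and by reason: use-related (missed visits, tampering) versus procedural (Deep Dives, EMA noncompliance, lost phones). A single rule counting all post-discharge urines as positive would penalize JITAI for unread lessons.
- Code a tampered specimen as positive, and leave incarceration and hospital pauses out of the scheduled set.
- Say whether any urine obtained during a 21-day discharge taper counts. Section G does not establish that such urines are collected.
- Report, beside the main result, the delta at which the conclusion changes, whether that result is positive or null.

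The cost is a paragraph of analysis-plan text, a coded discharge reason for each participant and a few more model runs. No participant procedure changes. The downside is that a claim about opioid use may have to be qualified.
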